### **4 SAMPLE SIZE**

180 subjects per group (360 subjects in the two groups) as participants in the treatment period.

[Rationale for sample size]

The Japanese phase II/III study [CL-0003] demonstrated the change in IRLS score (mean and standard deviation) at the end of treatment period (Week 12) as shown in Table 1. Of the randomized subjects, 11.8% in the placebo group and 17.5% in the 600 mg group were discontinued during the treatment period.

**Table 1: Change in IRLS score (mean and standard deviation) at the end of treatment period (i.e., Week 12 of study treatment) in the Japanese phase II/III study [CL-0003]: FAS**

	Placebo		ASP8825 600 mg	
	N	Mean (SD)	N	Mean (SD)
Week 12 (LOCF)	116	-8.96 (7.286)	120	-11.10 (7.921)
Week 12 (Treatment period completers)	105	-9.27 (6.996)	98	-11.54 (7.793)

SD: Standard Deviation. LOCF: Last Observation Carried Forward

In addition, a repeated measures analysis of variance of the data from the patients given placebo or ASP8825 600 mg in the Japanese phase II/III study [CL-0003] and included in the Full Analysis Set showed that the adjusted means of the change from baseline in IRLS score at the end of treatment period (Week 12) were -9.15 in the placebo group and -11.71 in the 600 mg group. The difference between the adjusted means from the two groups was -2.56.

On the basis of these results, the difference between treatment groups in the change from baseline in IRLS score at the end of treatment period (Week 12) as the primary endpoint of this study was assumed to be -2.56, with a standard deviation of 8.000 in both groups. Under these assumptions, to detect a statistically significant difference between gabapentin enacarbil and placebo using a 2-sample t-test with a two-sided significance level of 0.05 and a power of 80%, 155 subjects per group would be required. Assuming the discontinuation rate during the treatment period was approximately 15.0% in each group, the sample size has been set to 180 per group.

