**Table 2 Treatment groups**

Randomization Arm Code (ARMCD)	Randomization Arm (ARM)	Treatment Group (Labels in TLFs)	
G600	GABAPENTIN ENACARBIL 600 mg QD	Gabapentin enacarbil	Total
P	PLACEBO	Placebo	

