### **Compliance in Entire Period**

For each subject, compliance of study drug in entire period will be calculated in %, using the following formula:

$$\frac{\text{Total number of study drugs actually taken in entire period}}{\text{Duration of Exposure in Entire Period} \times 2} \times 100$$

where

‘Total number of study drugs actually taken in entire period’ =  
(Sum of “Number Dispensed” for -1WEEK, 0WEEK, 1WEEK, 2WEEK, 4WEEK,  
6WEEK, 8WEEK, 10WEEK and 12WEEK in the Study Drug Accountability 2 eCRF)  
minus (Sum of “Number Returned” for -1WEEK, 0WEEK, 1WEEK, 2WEEK, 4WEEK,  
6WEEK, 8WEEK, 10WEEK and 12WEEK in the Study Drug Accountability 2 eCRF)  
minus (Sum of “Number Lost” for -1WEEK, 0WEEK, 1WEEK, 2WEEK, 4WEEK,  
6WEEK, 8WEEK, 10WEEK and 12WEEK in the Study Drug Accountability 2 eCRF)

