## **7.4 Analysis of Efficacy**

### **7.4.1 Analysis of Primary Endpoint**

#### **7.4.1.1 Primary Analysis**

The primary analysis will be performed using the FAS.

The primary efficacy endpoint is the change from baseline in IRLS score at the end of treatment period. Using a repeated measures analysis of variance model, so-called Mixed Model of Repeated Measurements (MMRM) model, having the following average structure, the adjusted mean in each treatment group and its difference (gabapentin enacarbil group - placebo group) at the end of treatment period (Week 12) will be calculated, with comparison between the placebo group and the gabapentin enacarbil group:

Change in IRLS score at each time point

$$= \text{Baseline IRLS score} + \text{Age category}^{\ast 1} + \text{Estimated creatinine clearance category}^{\ast 2} + \\ \text{Treatment group} + \text{Time point} + \text{Treatment group} \times \text{Time point}$$

$\ast^1$  Age category: < 50 years and  $\geq$  50 years

$\ast^2$  Estimated creatinine clearance category:  $\geq$  60 to < 90 mL/min and  $\geq$  90 mL/min

Compound symmetry will be used as the covariance structure for repeated measures of the response variable. A two-sided significance level of 0.05 will be used for statistical tests.

The least-squares mean estimates of the change from baseline in IRLS score at Week 12, the estimates of treatment effect (e.g., least-squares mean change from baseline in IRLS score for gabapentin enacarbil group minus the least-squares mean change from baseline in IRLS score for placebo group) and the corresponding 95% CIs will be reported.

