## **MMRM**

The SAS procedure will be similar to the following:

```
proc mixed;  
  class SUBJECT GROUP VISIT AGE ECC;  
  model CHANGE = GROUP BASE VISIT AGE ECC GROUP*VISIT / ddfm=sat;  
  repeated VISIT /subject = SUBJECT type = cs;
```

```
lsmestimate  
  GROUP*VISIT  
  "GABAPENTIN ENACARBIL v.s. PLACEBO"  
  0 0 ... 0 1 0 0 ... 0 1 / cl alpha=0.05 om;  
  where VISIT in ('Week1', 'Week2', ... , 'Week12');  
run;
```

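### The SAP's example code for the primary contrast does not give the Week 12 active-minus-placebo difference: both coefficients are +1, and under default level order they may fall on Week 8

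*SAP*

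**What the plan says.** The governing text is clear. SAP 7.4.1.1 says that, from the repeated measures model, the adjusted mean in each arm and its "difference (gabapentin enacarbil group - placebo group) at the end of treatment period (Week 12) will be calculated". Protocol 7.4.1.1 defines the same comparison.

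The code under the MMRM heading is introduced with "The SAS procedure will be similar to the following", so it is illustrative. Its relevant parts are:

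- the class statement, "class SUBJECT GROUP VISIT AGE ECC", with no `ORDER=` option shown there or on `PROC MIXED`;
- an `LSMESTIMATE` on `GROUP*VISIT`, labelled as active versus placebo, with coefficients "0 0 ... 0 1 0 0 ... 0 1 / cl alpha=0.05 om";
- a visit filter that treats VISIT as text, beginning "where VISIT in ('Week1', 'Week2', ... , 'Week12".

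No other code is given for the primary estimate, confidence interval and p-value. SAP 7.4.1.2 repeats the primary analysis on the PPS, so the same contrast would be used there.

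**The concern.** A difference between two arms needs coefficients that sum to zero. The printed ones sum to 2, so the statement adds the two adjusted means. The resulting test asks whether that sum is zero, which says nothing about treatment.

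The second problem is position. The 1 sits in the last `GROUP*VISIT` cell of each arm, which is Week 12 only if Week 12 is the last level of VISIT. Text labels without leading zeros do not sort in time order, and `PROC MIXED` orders class levels by formatted value unless told otherwise.

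The two errors differ in how easily they show. A treatment effect near -21 on the IRLS would attract attention at once. A Week 8 difference would look entirely plausible. This trial was set up because the earlier Japanese study did not verify the 600 mg dose, so its one confirmatory contrast should leave no room for doubt.

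**Working it through.** **Inputs**

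- Week 12 adjusted means in the earlier Japanese study (SAP 4): -11.71 for 600 mg and -9.15 for placebo.
- Planning SD 8.000, two-sided alpha 0.05, 155 evaluable per arm, 180 randomized per arm, about 15% discontinuation (SAP 4).
- Treatment-period IRLS visits (Protocol 5.3): Weeks 1, 2, 4, 6, 8, 10 and 12.
- Arm codes (SAP Table 2): G600 and P.

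**The plan's own figures**

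- Difference: -11.71 - (-9.15) = -2.56. SAP 4 agrees: "The difference between the adjusted means from the two groups was -2.56".
- Sample size: the two-sample t-test with difference 2.56 and SD 8 has power 0.7993 at 154 per arm and 0.8019 at 155. The stated 155 is reproduced.
- Evaluable per arm at 15% loss: 180 × 0.85 = 153.

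**Sign**

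- Contrast as printed, if the last level is Week 12: (+1)(-11.71) + (+1)(-9.15) = -20.86.
- With no treatment effect (both arms at -9.15): -9.15 + (-9.15) = -18.30.
- Standard error: 8 × √(2/153) = 0.915. It is the same for a sum as for a difference when the arms are independent.
- -18.30 / 0.915 = -20.0, so the printed contrast would reject essentially always, even with no drug effect.

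**Visit order**

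The seven visits sort alphabetically as follows:

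| Label style | Where it appears | Sorted order |
|---|---|---|
| `Week1` | `WHERE` clause of the code | Week1, Week10, Week12, Week2, Week4, Week6, Week8 |
| `Week 1` | SAP 7.10.3.1 | Week 1, Week 10, Week 12, Week 2, Week 4, Week 6, Week 8 |
| `1WEEK` | SAP 6.3.1, Compliance in Entire Period ("6WEEK, 8WEEK, 10WEEK and 12WEEK in the Study Drug Accountability 2 eCRF") | 10WEEK, 12WEEK, 1WEEK, 2WEEK, 4WEEK, 6WEEK, 8WEEK |

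Week 8 is last in all three styles. In the style used by the code, Week 12 is third. The arms sort with the active arm first (G600 before P), so +1 then -1 does give active minus placebo.

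**What a Week 8 substitution could do**

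The documents give no Week 8 means, so the Week 8 effect is an assumption and is shown as a range. With SE 0.915 and 304 degrees of freedom:

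| Effect reported | Points | t | p |
|---|---|---|---|
| Week 12 as planned | -2.56 | -2.80 | 0.0055 |
| Week 8 at 60% of plan | -1.54 | -1.68 | 0.094 |
| Week 8 at 70% of plan | -1.79 | -1.96 | 0.051 |
| Week 8 at 140% of plan | -3.58 | -3.92 | 0.0001 |

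Each 1-point gap between the Week 8 and Week 12 effects moves t by 1 / 0.915 = 1.09. The significance limit is 1.80 points, about 70% of the planned effect.

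**The case against.** The strongest reply is that the code does not govern. It is offered only as similar to what will be run. It contains literal ellipses, so it cannot run as printed, and the text around it is unambiguous. A programmer who follows the text cannot report a sum. That stands, and it is why this is a code correction and not a criticism of the defined analysis.

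The minus sign may have been lost in extracting the PDF text. This cannot be excluded. Other minus signs survive in the same document, including those in SAP 4 and in the definition of the difference in 7.4.1.1, so a loss is less likely. The signed SAP will settle it. The visit-order point does not depend on the answer.

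The Week 8 problem needs VISIT to stay as unpadded text, no ordering option in the final program, and coefficients entered by position. The SAP fixes none of these. Its visit filter lists the weeks in time order, so the author plainly meant the last position to be Week 12. The `12WEEK` labels belong to the drug accountability form and not to the IRLS variable. All of this is fair, and the point is conditional for that reason.

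The Week 12 arm means that SAP 7.4.1.1 requires would also expose a Week 8 difference, as could the by-visit ANCOVA and the sensitivity analyses. They would, but only if someone subtracts the means or compares outputs from different models. The SAP names no such check.

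Finally, the 60% to 140% range has no support in the documents, and 0.915 is a planning standard error, not one from the repeated measures model. With all 180 per arm contributing, SE = 8 × √(2/180) = 0.843 and the limit falls to about 1.66 points, or 65% of plan. The p-values therefore show scale only and are not a forecast.

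**Conclusion.** The concern holds. As printed, the example contrast is a sum and not a difference: -20.86 instead of -2.56 on the plan's own means. Confidence in this is high for the text as extracted, subject to checking the minus sign in the signed SAP.

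The Week 8 point is held with moderate confidence. It applies if VISIT is analysed as unpadded text under default ordering. Its effect on the result cannot be sized from the documents. Under the assumed range and the planning standard error, a Week 8 effect below about 70% of plan would turn a significant Week 12 result into a non-significant reported one, and a larger Week 8 effect would overstate the evidence.

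The primary estimand, model and sample size are not affected. The code should be corrected before programming and unblinding.

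**What to change.** 1. Check the signed SAP for a minus sign before the second 1.
2. Make VISIT numeric (1, 2, 4, 6, 8, 10, 12), put `ORDER=INTERNAL` on `PROC MIXED`, and change the filter to `where VISIT in (1,2,4,6,8,10,12);`.
3. Replace the positional list with `lsmestimate GROUP*VISIT 'GE - placebo, Week 12' [1, 1 7] [-1, 2 7] / cl alpha=0.05 om;`.
4. Before use, confirm from the class-level output that GROUP level 1 is the active arm (SAP Table 2: "GABAPENTIN ENACARBIL 600 mg QD", code G600) and that VISIT level 7 is Week 12.
5. Check the estimate against the Week 12 difference from `lsmeans GROUP*VISIT / diff cl om;`.

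The `om` option can stay. Baseline, age and creatinine clearance enter the model without treatment interactions, so their weights cancel in the difference, although they can move the arm means.

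The cost is three lines of example code, one numeric visit variable and one cross-check, all before unblinding. Other correct programs would also serve, provided that the sign and the visit are fixed explicitly.

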### **7.4.1.2 Secondary Analysis**

The primary analysis will be repeated on the PPS. Additionally, the analysis to confirm the robustness will be presented.

### **7.4.1.3 Sensitivity Analysis**

The primary endpoint will be analyzed using the following approaches:

- Analysis of Covariance (ANCOVA) model with Last Observation Carried Forward (LOCF),
- Analysis of Covariance (ANCOVA) model with Multiple Imputation (MI), and
- Pattern Mixture Model (PMM) with different assumptions for missing patterns.

For all sensitivity analyses, confidence intervals will be presented.

Table 5 summarizes all sensitivity analyses to be performed with the primary endpoint.

**Table 5 Primary, Secondary and Sensitivity Analyses for Primary Endpoint**

Code	Set	Endpoint	Model	Covariates
Primary	FAS	Change from baseline in IRLS score at the end of treatment period (Week 12)	MMRM	Treatment group, Visit, Baseline IRLS score, Age category, Estimated creatinine clearance category, Visit by Treatment group interaction
Secondary	PPS	Change from baseline in IRLS score at the end of treatment period (Week 12)	MMRM	Treatment group, Visit, Baseline IRLS score, Age category, Estimated creatinine clearance category, Visit by Treatment group interaction
S1	FAS	Change from baseline in IRLS score at the end of treatment period (Week 12)	ANCOVA with LOCF	Treatment group, Baseline IRLS score, Age category, Estimated creatinine clearance category
S2	FAS	Change from baseline in IRLS score at the end of treatment period (Week 12)	ANCOVA with MI	Treatment group, Baseline IRLS score, Age category, Estimated creatinine clearance category
S3	FAS	Change from baseline in IRLS score at the end of treatment period (Week 12)	PMM (Last Mean Carried Forward)	Treatment group, Baseline IRLS score, Age category, Estimated creatinine clearance category
S4	FAS	Change from baseline in IRLS score at the end of treatment period (Week 12)	PMM (Last Mean Carried Forward for Gabapentin Enacarbil and Randomized Arm MAR for Placebo)	Treatment group, Baseline IRLS score, Age category, Estimated creatinine clearance category
S5	FAS	Change from baseline in IRLS score at the end of treatment period (Week 12)	PMM (Copy Reference)	Treatment group, Baseline IRLS score, Age category, Estimated creatinine clearance category
S6	FAS	Change from baseline in IRLS score at the end of treatment period (Week 12)	PMM (Jump to Reference)	Treatment group, Baseline IRLS score, Age category, Estimated creatinine clearance category
S7	FAS	Change from baseline in IRLS score at the end of treatment period (Week 12)	PMM (Copy Increment from Reference)	Treatment group, Baseline IRLS score, Age category, Estimated creatinine clearance category

### **ANCOVA with MI**

The MI ANCOVA model will be used to compare gabapentin enacarbil and placebo group in a fixed sequence procedure:

1. Generate 1000 datasets, using seed 394852, where intermittent missing IRLS score will be imputed for each treatment relying on non-missing data from all subjects within each treatment group using the Monte Carlo Markov Chain (MCMC) imputation model with treatment and the available non-missing IRLS score for each scheduled Week. The MCMC statement in the SAS PROC MI procedure with monotone option will be used. As a result, each dataset will only have missing ending data, or a monotone missing data pattern.
2. For each dataset from step 1, missing ending data (IRLS score up through end of treatment period) will be imputed using seed 394852. As a result, 1000 imputed complete datasets will be generated.
  - Missing data at Week 1 will be imputed using the regression imputation model with the stratification factors, baseline and IRLS score from Week 1, using the SAS PROC MI procedure with the REGRESSION option in the MONOTONE statement.
  - The SAS PROC MI procedure will use data separately from each treatment subjects to impute the missing data for a specific Week (i.e., only those that need the imputation for the Week). Since subjects from the different treatment groups for that Week are excluded from the step, they will not contribute to the imputation for the Week.
  - Repeat for all other scheduled Weeks sequentially (Week 2 to the end of evaluation period). Subjects whose missing data were imputed for previous Weeks will contribute to the imputation for the current Week.

The regression imputation model includes an intercept and the slopes of the IRLS score from previous Weeks and the stratification factors.

3. Analyze each imputed dataset using the ANCOVA using the observed or imputed IRLS score at Week 12. The model will contain terms for baseline IRLS score measurement as a covariate and treatment group and the other stratification factors as fixed effects.
4. Combine estimates from the results of each of the 1000 ANCOVA runs using SAS PROC MIANALYZE.

The least-squares mean estimates of the change from baseline in IRLS score at Week 12, the estimates of treatment effect (e.g., least-squares mean change from baseline in IRLS score for gabapentin enacarbil group minus the least-squares mean change from baseline in IRLS score for placebo group) and the corresponding 95% CIs will be reported.

### **Pattern Mixture Models (PMM)**

PMMs will be used as an alternative to impute missing values, using different assumptions for missing patterns.

PMMs provide a general and flexible framework for sensitivity analyses that allows formulating assumptions regarding missing data in a transparent and clinically interpretable manner. This is expected to address the possibility of the data being missing not at random (MNAR).

The following aspects of data missingness, may affect the estimates.

- Timing and extent of missingness
- Assumed underlying mechanism for data missingness

#### **A. Timing and Extent of Missing Data**

To assess the potential effect of data missingness on the estimate of treatment effect, subjects will be classified as full data or missing data cases. Patterns of missingness will be based on non-missing IRLS score before the end of the treatment period.

- Full data cases are defined as subjects with non-missing IRLS score for all scheduled weeks of the treatment period.
- Missing data cases are defined as subjects with a missing IRLS score on at least one scheduled Week of the treatment period. The missing data cases are further grouped into intermittent missing and monotone missing cases.
  - Intermittent missing hemoglobin cases are defined as subjects with a missing IRLS score for at least one scheduled week of but not on consecutive scheduled weeks up to end of the treatment period.
  - Monotone missing IRLS score cases are defined as subjects who have consecutive scheduled Weeks with missing IRLS score up to the end of treatment period. A subject who is a Monotone missing case could have intermittent missing IRLS score prior to the ending Week.

Subjects will be grouped as follows:

- Full data cases
- Intermittent missing data cases
- Monotone missing data cases

Should the incidence of Monotone missing data cases and intermittent missing data cases be relatively small, then those cases will be combined so that the groups are full data cases and missing data cases.

#### **B. Assumptions on Missing Data Mechanism**

In addition to the extent of data missingness, the mechanism under which missing data occur may affect the estimate of the parameter of interest.

The potential impact of missing efficacy endpoints on the estimates of treatment effects will be assessed using alternative statistical models with different underlying assumptions on the missing data mechanism for MNAR (Little and Rubin, 2002).

#### **C. PMM - Last Mean Carried Forward**

A pattern-mixture model using a last mean carried forward multiple imputation method (Carpenter *et al.*, 2013) will be used as another sensitivity analysis to explore the robustness of the MMRM, ANCOVA with LOCF and ANCOVA with MI results for the primary efficacy variables. Using this method, missing data after ending week will be imputed based on the last non-missing mean from its own treatment group.

#### **D. PMM - Last Mean Carried Forward for Gabapentin Enacarbil and Randomized Arm MAR for Placebo**

This method is a combination of PMM-Last Mean Carried forward for gabapentin enacarbil and PMM-Randomized Arm MAR for placebo group. The imputation data will be generated based on last mean carried forward method described above for the gabapentin enacarbil group, while for the placebo group, the imputation data will be generated using the Randomized Arm MAR group described below.

The Randomized Arm MAR is similar to PMM-Last Mean Carried Forward except that the joint distribution of the patient's observed and missing data is multivariate normal with mean and covariance matrix from their randomized arms.

#### **E. PMM - Copy Reference**

For the purpose of imputing the missing response data, a patient's whole distribution, both pre- and post-discontinuation, is assumed to be the same as placebo group. Post-discontinuation data in the placebo group will be imputed under Randomized Arm MAR.

#### **F. PMM - Jump to Reference**

For post-discontinuation, subject's mean response distribution is assumed to be the same as that of the placebo group. Such a change may be seen as extreme, and choosing the placebo group might be used as a worst-case scenario in terms of reducing any treatment effect since withdrawn patients on active will lose the effect of their period on treatment. Post-discontinuation data in the reference arm will be imputed under Randomized Arm MAR.

#### **G. PMM - Copy Increment from Reference**

After the subject discontinuation, the subject's post-discontinuation mean increments copy those from the placebo group. Post-discontinuation data in the placebo arm will be imputed under Randomized Arm MAR.

#### **H. Analysis Model and Reporting**

The ANCOVA model will then be performed for each combined imputed complete data set. Similarly, the Rubin's method will be then used to combine the estimates and the differences between the least square mean differences between the two treatment groups from each of the ANCOVA analyses.

The least-squares mean estimates of the change from baseline in IRLS score at Week 12, the estimates of treatment effect (e.g., least-squares mean change from baseline in IRLS score for gabapentin enacarbil group minus the least-squares mean change from baseline in IRLS score for placebo group) and the corresponding 95% CIs will be reported.

## **7.4.2 Analysis of Secondary Endpoints**

The analyses of secondary endpoints will be performed using the FAS.

### **7.4.2.1 Change from baseline in IRLS score at each time point**

The baseline visit is the measurement at Week 0.

IRLS score and its change from baseline will be summarized by descriptive statistics, by treatment group and visit.

Least square mean difference (gabapentin enacarbil group minus placebo group) of the changes in IRLS score from baseline will be calculated by visit, using ANCOVA model with the baseline value as a covariate. 95% CI and two-sided p-value of the difference will be presented.

Change from baseline in IRLS score will be summarized by subgroups defined in section 7.8.

Following data will be presented graphically by treatment group:

- IRLS score using mean (+/- SD) plot,
- Change in IRLS score from baseline using mean (+/- SD) plot.

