7.1 Sample Size

180 subjects per group (360 subjects in the two groups) as participants in the treatment period

[Rationale for the sample size]

The Japanese phase II/III study [CL-0003] demonstrated the change in IRLS score (mean and standard deviation) at the end of treatment period (Week 12) as shown in Table 8. Of the randomized subjects, 11.8% in the placebo group and 17.5% in the 600 mg group were discontinued during the treatment period.

Table 8: Change in IRLS score (mean and standard deviation) at the end of treatment period (i.e., Week 12 of study treatment) in the Japanese phase II/III study [CL-0003]: FAS

	Placebo		ASP8825 600 mg	
	N	Mean (SD)	N	Mean (SD)
Week 12 (LOCF)	116	-8.96 (7.286)	120	-11.10 (7.921)
Week 12 (Treatment period completers)	105	-9.27 (6.996)	98	-11.54 (7.793)

SD: Standard Deviation. LOCF: Last Observation Carried Forward

In addition, a repeated measures analysis of variance of the data from the patients given placebo or ASP8825 600 mg in the Japanese phase II/III study [CL-0003] and included in the

Full Analysis Set showed that the adjusted means of the change from baseline in IRLS score at the end of treatment period (Week 12) were -9.15 in the placebo group and -11.71 in the 600 mg group. The difference between the adjusted means from the two groups was -2.56 .

On the basis of these results, the difference between treatment groups in the change from baseline in IRLS score at the end of treatment period (Week 12) as the primary endpoint of this study was assumed to be -2.56 , with a standard deviation of 8.000 in both groups. Under these assumptions, to detect a statistically significant difference between gabapentin enacarbil and placebo using a 2-sample t-test with a two-sided significance level of 0.05 and a power of 80% , 155 subjects per group would be required. Assuming the discontinuation rate during the treatment period was approximately 15.0% in each group, the sample size has been set to 180 per group.

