### **7.4.2.4 Change from baseline in Pittsburgh Sleep Quality Index at each time point**

The baseline visit is the measurement at Week 0.

PSQI component scores (sleep quality, sleep latency, sleep duration, habitual sleep efficiency, sleep disturbance, use of sleeping medication, and daytime dysfunction) and PSQI

global score, and their change from baseline will be summarized by descriptive statistics, by treatment group and visit.

Least square mean difference (gabapentin enacarbil group minus placebo group) of the changes in PSQI component and global scores from baseline will be calculated by visit, using the ANCOVA model with the baseline value as a covariate. 95% CI and two-sided p-value of the difference will be presented.

Following data will be presented graphically by treatment group:

- PSQI component scores (sleep quality, sleep latency, sleep duration, habitual sleep efficiency, sleep disturbance, use of sleeping medication, and daytime dysfunction) and PSQI global score using mean (+/- SD) plot,
- Change in PSQI component scores (sleep quality, sleep latency, sleep duration, habitual sleep efficiency, sleep disturbance, use of sleeping medication, and daytime dysfunction) and PSQI global score from baseline using mean (+/- SD) plot.

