#### **7.4.2.5 Change from baseline in Athens Insomnia Scale at each time point**

The baseline visit is the measurement at Week 0.

Total score of Athens insomnia scale and its change from baseline will be summarized by descriptive statistics, by treatment group and visit.

Least square mean difference (gabapentin enacarbil group minus placebo group) of the changes in total score of Athens insomnia scale from baseline will be calculated by visit, using the ANCOVA model with the baseline value as a covariate. 95% CI and two-sided p-value of the difference will be presented.

Following data will be presented graphically by treatment group:

- Total score of Athens insomnia scale using mean (+/- SD) plot,
- Change in total score of Athens insomnia scale from baseline using mean (+/- SD) plot.

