#### **7.4.2.6 Change from baseline in RLS Pain score at each time point**

The baseline visit is the measurement at Week 0.

RLS pain score and its change from baseline will be summarized by descriptive statistics, by treatment group and visit.

Least square mean difference (gabapentin enacarbil group minus placebo group) of the changes in RLS pain score from baseline will be calculated by visit, using the ANCOVA model with the baseline value as a covariate. 95% CI and two-sided p-value of the difference will be presented.

Following data will be presented graphically by treatment group:

- RLS pain score using mean (+/- SD) plot,
- Change in RLS pain score from baseline using mean (+/- SD) plot.

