### **7.10.1 Missing Data**

As a general principle, no imputation of missing data will be done. Exception is the primary efficacy endpoint. The following imputations will be performed:

- An MMRM model will be run for the purpose of implicit imputation of missing data by using all the available information from the observed data via the within-patient correlation structure for continuous endpoints with inferential analysis (section 7.4.1.1).
- An ANCOVA model with Last Observation Carried Forward (LOCF), an ANCOVA model with multiple imputations (MI) and PMM models with different missingness patterns assumptions will be run as the sensitivity analysis for the primary analysis (section 7.4.1.3).

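### By-visit tests of IRLS, PSQI, Athens and RLS Pain use observed cases only, so response-related dropout would bias them, and Week 12 IRLS gets a second p-value by a method that differs from the primary MMRM

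*SAP*

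**What the plan says.** **Secondary tests.** SAP 7.4.2.1 states that the IRLS difference "will be calculated by visit, using ANCOVA model with the baseline value as a covariate". The same wording covers three other scales: "changes in PSQI component and global scores from baseline will be calculated by visit" (SAP 7.4.2.4), "changes in total score of Athens insomnia scale from baseline will be calculated by visit" (7.4.2.5) and "changes in RLS pain score from baseline will be calculated by visit" (7.4.2.6). Baseline is the only covariate named. Each test uses the FAS and gives a 95% CI and a two-sided p-value. Protocol 7.4.2 also names ANCOVA for these endpoints and does not say there how missing values are handled.

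**Missing data.** SAP 7.10.1 states: "As a general principle, no imputation of missing data will be done. Exception is the primary efficacy endpoint". A Week 12 ANCOVA therefore uses only subjects with a value in the Day 82 to 88 window.

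**Primary analysis.** SAP 7.4.1.1 fits an MMRM to the same Week 12 IRLS change in the same FAS. It includes baseline, both stratification factors, treatment, visit and treatment × visit, with compound symmetry. Every analysis in SAP Table 5 includes the stratification factors.

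**Two unclear places.** SAP 7.10.1 describes the MMRM as working "via the within-patient correlation structure for continuous endpoints with inferential analysis", but refers only to section 7.4.1.1. SAP 7.10.3.1 and 7.10.3.3 define an End of treatment visit for all four scales, and the SAP does not say whether the by-visit ANCOVA is also run on it.

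**The concern.** An ANCOVA at a single visit conditions only on arm and baseline. It is unbiased if, given those, being observed at that visit is unrelated to the score there. The primary MMRM needs less: missingness may also depend on scores already observed after baseline. A subject who leaves at Week 6 after responding poorly informs the MMRM's Week 12 estimate through the earlier visits, but contributes nothing to the Week 12 ANCOVA. The secondary tests thus rest on a stricter assumption than the trial's own primary model.

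Two things are at stake. The sleep and pain effects, and the later IRLS visits, could be misstated in size. The report would also carry two p-values for Week 12 IRLS change in the FAS, from models with different missing-data assumptions and covariates, and these could disagree.

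**Working it through.** **1. The plan's own figure.** Protocol 7.1 and SAP 4 assume a difference of 2.56, SD 8.0, two-sided 0.05 and 80% power. The two-sample t-test solution is 154.26, rounded up to the stated 155. Inflating for 15% dropout gives 155/0.85 = 182.4. The stated 180 leaves 180 × 0.85 = 153 per arm and about 79.7% power. That shortfall is immaterial to this point.

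**2. Subjects absent at Week 12.** The CL-0003 rates (Protocol 7.1) are 11.8% placebo and 17.5% on 600 mg.
- Placebo: 180 × 0.118 = 21.2 absent, about 159 observed.
- Active: 180 × 0.175 = 31.5 absent, about 149 observed.

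**3. Was dropout related to response in CL-0003?** The LOCF and completer rows of Protocol Table 8 imply the last-observed mean of the rest:
- Placebo: (116 × −8.96 − 105 × −9.27)/11 = −6.0, against −9.27 in completers (3.27 worse).
- 600 mg: (120 × −11.10 − 98 × −11.54)/22 = −9.14, against −11.54 (2.40 worse).

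The Week 12 differences are −2.14 (LOCF), −11.54 + 9.27 = −2.27 (completers) and −11.71 + 9.15 = −2.56 (repeated measures).

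**4. Simple bias formula.** Let d be an arm's dropout proportion and D the amount by which leavers' Week 12 mean would be worse than completers'. The completer mean equals the full mean minus d × D. The bias in the difference (active − placebo) is therefore −d(active) × D(active) + d(placebo) × D(placebo).
- D = 0 in both arms: no bias, however unequal the rates.
- D = 5 in both arms: −0.175 × 5 + 0.118 × 5 = −0.29.
- D = 5 in placebo only: 0.118 × 5 = +0.59.
- D = 5 in active only: −0.175 × 5 = −0.88.
- Step 3 gaps taken at face value: −0.175 × 2.40 + 0.118 × 3.27 = −0.03.

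**5. Simulation.** Taken from the documents: 180 per arm, seven post-baseline IRLS visits, true Week 12 difference −2.56, SD 8, dropout 11.8%/17.5% unless stated. Assumed: the mean trajectory; correlation (compound symmetry 0.6, or AR(1) 0.85 per visit step); every subject observed at Week 1; and a logistic dropout model on the IRLS score, with slope 1 per 8 points when shared by both arms and 1.5 when in one arm only. Under MAR dropout depends on the previous score, under MNAR on the current one. There were 300 runs per scenario, and the Monte Carlo SE of each mean is about 0.05. The MMRM used compound symmetry, without stratification factors.

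| Dropout mechanism | Full data | By-visit ANCOVA | MMRM | ANCOVA − full | MMRM − full |
|---|---|---|---|---|---|
| Unrelated to outcome | −2.50 | −2.51 | −2.54 | −0.01 | −0.04 |
| MAR, same in both arms | −2.46 | −2.73 | −2.48 | −0.27 | −0.02 |
| MAR, poor responders leave placebo only | −2.59 | −1.75 | −2.57 | +0.84 | +0.02 |
| MAR, poor responders leave active only | −2.60 | −3.71 | −2.61 | −1.11 | −0.01 |
| Equal 15%/15%, MAR in placebo only | −2.63 | −1.66 | −2.64 | +0.97 | −0.01 |
| MNAR, placebo only | −2.59 | −1.76 | −2.35 | +0.83 | +0.24 |

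With AR(1) data and the planned compound symmetry, across the three MAR patterns at 11.8%/17.5% dropout, the MMRM was off by 0.06 to 0.20 and the ANCOVA by 0.28 to 1.05.

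**The case against.** **Discontinued subjects are not lost altogether.** A reader might infer that the ANCOVAs drop them entirely. They do not. Such subjects count at every visit before leaving. All four scales are collected at discontinuation (Protocol 5.3), so that value counts if it falls in a visit window. They may also enter the End of treatment row. This stands. But that row is a last on-treatment value, does not estimate Week 12, and may not be tested.

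**Unequal dropout is not itself the cause.** The 11.8%/17.5% imbalance invites that inference. The first simulation row shows no bias with unequal rates, and the 15%/15% row shows about 1 point with equal rates. What matters is dependence on response.

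**The CL-0003 evidence is soft.** The leavers' means rest on 11 and 22 subjects and on last observations, often early ones. IRLS improves with time on study (Protocol Table 7: −4.4 at Week 1, −9.4 at Week 4), so part of the gap would appear under random dropout. The gap is in the same direction in both arms, which points to the small end of the range, and the face-value calculation gives almost nothing. The 0.29-point gap between −2.27 and −2.56 sets unadjusted against adjusted means, and the completer difference alone has SE √(6.996²/105 + 7.793²/98) = 1.04. It cannot be read as an 11% dropout bias.

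**The MMRM is not immune.** It leaves error under MNAR or a wrong covariance. PSQI and Athens are first measured after baseline at Week 4, so little is recovered for subjects who leave earlier.

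**SAP 7.10.1 need not contradict the secondary sections.** The phrase on continuous endpoints follows an exception for the primary endpoint and cites only 7.4.1.1. It is ambiguous, not a broken commitment. Table 5 is confined to the primary endpoint, so the absence of a secondary analysis from it is not an omission.

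ANCOVA is also prespecified in the protocol. None of this removes the stricter missing-data assumption or the second Week 12 p-value.

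**Conclusion.** The point holds as an inexpensive improvement to the secondary analyses. Bias in the by-visit ANCOVAs is conditional on dropout depending on post-baseline response, which CL-0003 makes plausible but does not prove. Its simulated size at Week 12 for IRLS is about 0.3 points (0.27/2.56, roughly 10%) if the mechanism is shared by the arms. It is 0.8 to 1.1 points, in either direction, if the mechanism operates in one arm only. These sizes rest on the assumed correlations, trajectory and dropout slopes. The documents give no SDs for PSQI, Athens or RLS Pain, so no size is claimed for them.

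The duplicate Week 12 IRLS test does not depend on any simulation: it follows from the text. A reader might infer that the primary result is in doubt. It is not. SAP 7.4.1.1 identifies the primary analysis clearly, and seven sensitivity analyses in Table 5 address its missing data.

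**What to change.** 1. **IRLS (SAP 7.4.2.1).** Report each visit's difference, CI and p-value from the treatment × visit contrasts of the primary MMRM. Remove the Week 12 ANCOVA p-value, or label it as a supplementary observed-case analysis.
2. **PSQI, Athens, RLS Pain (SAP 7.4.2.4 to 7.4.2.6).** Fit a repeated-measures model of the same form (the scale's own baseline, both stratification factors, treatment, visit, treatment × visit) and take each visit's contrast from it.
3. **Wording.** In SAP 7.10.1, state which endpoints the MMRM sentence covers. State whether and how the End of treatment row is analysed.
4. Keep the descriptive tables and plots.

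**Cost.** No new data. The treatment × visit term is already in the SAP's MMRM code, so IRLS needs only extra contrasts, and the same code serves the other scales. Because Protocol 7.4.2 names ANCOVA, the change needs a short SAP/CSR note or a small amendment before unblinding.

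**Limits.** This largely reduces the bias under MAR. It does not remove it if data are MNAR or compound symmetry is wrong, and it recovers little for PSQI and Athens in subjects who leave before Week 4.
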